Variables:	
For all three cohorts receiving empagliflozin, the baseline values of the following variables will be assessed:
 
 • Age (<65; 65 – <75; 75 – 80 , >80) • Gender • Weight [kg] • Height [cm] • HbA1c [% or mmol/ mol], FPG (available in subgroup only) • Previous occurrence of 
 ◦ Typical CV comorbidities: 
 ▪ MI ▪ Stroke ▪ CAD ▪ PAD ▪ CHF (form (HFrEF/ HFpEF) ◦ Other typical diabetes complications 
 ▪ Neuropathy ▪ Nephropathy / Renal function (eGFR, micro-/ macroalbuminuria) ▪ Diabetic foot syndrome ▪ Retinopathy (background and proliferative) • Antidiabetic and cardiovascular co-medication (lipid-lowering agents, RAAS blockers, other antihypertensives, beta blockers, diuretics, antiplatelets and anticoagulants) • Duration of diabetes (time since diagnosis) • Previous glucose-lowering treatment • Dosage of empagliflozin (10mg vs 25mg) (available in subgroup only) • Participation in Disease Management Programme (DMP) Type 2 Diabetes (from DPV registry) • Hospitalizations (from DPV registry)
Data sources:	
Data will be provided by the largest German T2D patient registries DPV& DIVE covering more than 500,000 patients.
 
The aim of the DPV initiative is to improve treatment outcomes in individuals with diabetes through standardized documentation and objective comparison of quality indicators as well as through multi-centre outcome research. Up to date, there are more than 400 centres participating in the initiative predominantly from Germany and from Austria.
 
DIVE is a national initiative for quality management of diabetes care. The aim is to transfer the already existing initiatives and software systems which collect patient-related data to a national diabetes registry. The DIVE registry is one of the biggest, most updated diabetes registries in Germany and part of the current development of a national diabetes registry. It is part of the first and second registry conference held by German Federal Ministry of Health (BMG) and Robert-Koch Institute (RKI).

Study size:	There will be about 7,900 patients on Empagliflozin included in the analysis.

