Data analysis:	
Variables will be assessed in half-yearly periods after index date (date of first prescription of empagliflozin), for total study population and separated by study cohort.
 
Anonymized data from the DIVE and the DPV registries will be combined; nonparametric descriptive analyses will be used. Group comparison will be based on Wilcoxon rank sum test (continuous variables) and X²-test for binary/categorial values. Analysis will be implemented using SAS 9.4. Complete case analysis will be used.
 
Analysis will be done by an experienced biostatistician with detailed knowledge of the DIVE and the DPV registries. A second independent programmer will check the generated SAS code for inconsistencies. The medical team (
 
will evaluate the results from a clinical background to ensure plausibility.
 
Quality assurance and control will be the responsibility of the medical team (

Milestones:	
 • Project kick-off: 09 November 2018 • Draft of study protocol: 5 July 2019 • Final study protocol & approval by: 31 August 2019 • Start of data access/data validation: 01 September 2019 • End of data analysis by: 31 October 2019 • Final report of study results by: 31 December 2019 • Finalization of publication draft by: 31 December 2019

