9. RESEARCH METHODS

9.1 STUDY DESIGN

Retrospective non-interventional cross-sectional study using real-world data from German patient registries. Data will be provided by the largest German T2D patient registries DPV& DIVE covering more than 500,000 patients. An anonymized dataset will be delivered by DIVE and DPV, respectively. The two datasets will then be combined.

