9.2 SETTING AND INCLUSION/EXCLUSION CRITERIA

Description of the real-life treatment of adult patients with T2DM receiving empagliflozin, comparing the characteristics of patients starting empagliflozin in three time intervals:

- The first analysis will include the patients receiving Empagliflozin before the EMPA-REG-OUTCOME study was published (time until mid-Sept. 2015; “Cohort 1”).
- The second analysis will include patients receiving Empagliflozin starting from the EMPA-REG-OUTCOME study being published until CV Label Change (time from mid-Sept. 2015-mid-Jan. 2017; “Cohort 2”).
- The third analysis will include all patients receiving Empagliflozin starting from mid-Jan. 2017 until last available data cut (“Cohort 3”).

Inclusion criteria:

- At least two outpatient T2DM diagnoses (ICD E11.-) in two different quarters and/or at least one inpatient T2DM diagnosis (ICD E11.-)
- At least one prescription of an empagliflozin-containing antidiabetic drug: Jardiance® (Empagliflozin, ATC A10BK03, former A10BX12) or Synjardy® (Empagliflozin/ Metformin, ATC A10BD20)

Exclusion criteria

- Any diagnosis of T1DM

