9.7 DATA ANALYSIS

9.7.1 Main analysis

Variables will be assessed in half-yearly periods after index date (date of first prescription of empagliflozin), for total study population and separated by study cohort.

Anonymized data from the DIVE and the DPV registries will be combined; nonparametric descriptive analyses will be used. Group comparison will be based on Wilcoxon rank sum test (continuous variables) and X²-test for binary/categorial values. Analysis will be implemented using SAS 9.4. Complete case analysis will be used.

Analysis will be done by an experienced biostatistician with detailed knowledge of the DIVE and the DPV registries. A second independent programmer will check the generated SAS code for inconsistencies. The medical team (

will evaluate the results from a clinical background to ensure plausibility.

Quality assurance and control will be the responsibility of the medical team (

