3.3 Does the protocol specify measures of occurrence? (e.g. incidence rate, absolute risk)				9.7

¹ Date from which information on the first study is first recorded in the study dataset or, in the case of secondary use of data, the date from which data extraction starts.

² Date from which the analytical dataset is completely available.

Section 3: Study design	Yes	No	N/A	Section Number
3.4 Does the protocol specify measure(s) of association? (e.g. relative risk, odds ratio, excess risk, incidence rate ratio, hazard ratio, number needed to harm (NNH) per year)				9.7
3.5 Does the protocol describe the approach for the collection and reporting of adverse events/adverse reactions? (e.g. adverse events that will not be collected in case of primary data collection)				(11)

Comments:

--

Section 4: Source and study populations	Yes	No	N/A	Section Number
4.1 Is the source population described?				9.4
4.2 Is the planned study population defined in terms of:				9.2
4.2.1 Study time period?				9.2
4.2.2 Age and sex?				9.2
4.2.3 Country of origin?				9.2
4.2.4 Disease/indication?				9.2
4.2.5 Duration of follow-up?				9.2
4.3 Does the protocol define how the study population will be sampled from the source population? (e.g. event or inclusion/exclusion criteria)				9.2

Comments:

--

Section 5: Exposure definition and measurement	Yes	No	N/A	Section Number

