5.1 Does the protocol describe how the study exposure is defined and measured? (e.g. operational details for defining and categorizing exposure, measurement of dose and duration of drug exposure)				-
5.2 Does the protocol address the validity of the exposure measurement? (e.g. precision, accuracy, use of validation sub-study)				-
5.3 Is exposure classified according to time windows? (e.g. current user, former user, non-use)				-
5.4 Is exposure classified based on biological mechanism of action and taking into account the pharmacokinetics and pharmacodynamics of the drug?				-

Comments:

As this is a cross-sectional study, there will be no follow-up period and thus no exposure measurement. A patient will be included after the first available record of drug use.

Section 6: Outcome definition and measurement	Yes	No	N/A	Section Number
6.1 Does the protocol specify the primary and secondary (if applicable) outcome(s) to be investigated?				9.3
6.2 Does the protocol describe how the outcomes are defined and measured?				9.3
6.3 Does the protocol address the validity of outcome measurement? (e.g. precision, accuracy, sensitivity, specificity, positive predictive value, prospective or retrospective ascertainment, use of validation sub-study)				9.8
6.4 Does the protocol describe specific endpoints relevant for Health Technology Assessment? (e.g. HrQoL, QALYs, DALYs, health care services utilization, burden of disease, disease management)				9.3

Comments:

--

Section 7: Bias	Yes	No	N/A	Section Number
7.1 Does the protocol describe how confounding will be addressed in the study?				

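### The half-yearly analysis contradicts the baseline-only design and, if carried out, has no last period or minimum follow-up, so Cohort 3 narrows progressively to its earlier starters

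*Combined protocol and SAP*

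**What the plan says.** The timing of measurement is set in section 9.7.1 and repeated in the abstract under Data analysis: "Variables will be assessed in half-yearly periods after index date", the index date being the first empagliflozin prescription. Results are to be given "for total study population and separated by study cohort". Neither place gives the number of periods, a last period or a minimum observation time.

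Section 9.2 admits patients on diagnosis criteria plus one prescription. Cohorts 1 and 2 have closed entry windows. Cohort 3 takes patients "starting from mid-Jan. 2017 until last available data cut", with no date for that cut.

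Other parts of the protocol describe a different study:

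- Section 9.1: "Retrospective non-interventional cross-sectional study using real-world data from German patient registries".
- Abstract, Variables: "the baseline values of the following variables will be assessed".
- Annex 2, comment to checklist section 5: "there will be no follow-up period and thus no exposure measurement".

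Annex 2 also ticks Yes for item "4.2.5 Duration of follow-up" and refers to section 9.2, which gives no duration.

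**The concern.** The programmer will work from section 9.7.1, and that section asks for follow-up tables which the design section, the abstract and the checklist exclude.

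If the tables are made, a patient can complete half-year k only if treatment began at least 6k months before the data cut. This restriction falls first and most heavily on Cohort 3, the only cohort whose entry runs up to the cut. Its later periods therefore describe an ever earlier slice of its starters, while Cohorts 1 and 2 lose few or none. Complete-case analysis without imputation neither causes nor repairs this.

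The study asks how patients starting in three intervals differ. If characteristics move with start date inside Cohort 3, its half-yearly series can drift although no patient changes, and the drift could be read as change on treatment. The pooled series can drift for the simpler reason that Cohort 3 drops out of the mix.

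**Working it through.** The plan states no figure to reproduce. The check is calendar arithmetic.

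**Inputs from the protocol.** Cohort 2 runs from mid-September 2015 to mid-January 2017, and Cohort 3 from mid-January 2017 to the cut (section 9.2). The abstract milestones give "Start of data access/data validation: 01 September 2019" and an end of analysis by 31 October 2019.

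**Assumptions.** Mid-month is the 15th and a month is 30.44 days. The central cut is 1 September 2019, with a range from 31 December 2018 to 31 October 2019. Starts are uniform within each cohort. As a sensitivity case the start rate doubles over the Cohort 3 window, because section 7 says SGLT2i use is rising.

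**Formulas.** T is the number of months from 15 January 2017 to the cut. It is the longest possible observation in Cohort 3 and the shortest in Cohort 2, whose window is 16.03 months.

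- Cohort 3 share completing half-year k, uniform starts: x = (T − 6k)/T, or 0 if negative.
- The same with a doubling start rate: (x + x²/2)/1.5.
- Cohort 2 share: min(1, (T + 16.03 − 6k)/16.03).

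**Central cut, T = 31.5.** The Cohort 3 shares are 25.5/31.5, 19.5/31.5, 13.5/31.5, 7.5/31.5 and 1.5/31.5, that is 81, 62, 43, 24 and 5%. With a doubling start rate they are 76, 54, 35, 18 and 3%. Every Cohort 2 patient has at least 31.5 months of calendar time and every Cohort 1 patient at least 47.5, so both stand at 100% through half-year 5.

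**Other cuts, uniform starts:**

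| Cut | T | Half-year 4: Cohort 3 v 2 | Half-year 5: Cohort 3 v 2 |
|---|---|---|---|
| 31 Dec 2018 | 23.49 | 0% v 97% | 0% v 59% |
| 30 June 2019 | 29.44 | 18.5% v 100% | 0% v 96.5% |
| 31 Oct 2019 | 33.48 | 28% v 100% | 10% v 100% |

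Cohort 1 loses nobody through half-year 6 at any of these cuts. If any part of a half-year counts instead of a completed one, every share moves one period later.

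**Pooled series.** Suppose a characteristic is constant at 25, 30 and 35% in Cohorts 1, 2 and 3 (illustrative). With cohort weights w1, w2, w3 and Cohort 3 share s, the total is (25w1 + 30w2 + 35w3s)/(w1 + w2 + w3s). From index (s = 1) to half-year 5 (s = 0.048) it moves:

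- from 30.0 to 27.7% with equal thirds,
- from 31.0 to 28.5% with a 20/40/40 split,
- from 32.5 to 29.2% with 10/30/60.

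No patient changes in any of these.

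**Cohort 3 minus Cohort 2.** Suppose a step at the cohort boundary plus a linear trend across the Cohort 3 window (illustrative). The difference at half-year k is step + slope × x/2. Three cases give 5.0 points at index. At half-year 4 (x = 0.238):

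- step 0, slope 10: 10 × 0.238/2 = 1.2 points;
- step 5, slope 0: 5.0 points;
- step 7.5, slope −5: 7.5 − 5 × 0.238/2 = 6.9 points.

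The distortion can shrink the difference, leave it alone or enlarge it.

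**The case against.** The strongest reply is that the half-yearly sentence is the odd one out. The design is called cross-sectional, the abstract speaks of baseline values, the checklist denies any follow-up, and the objective compares patients at the start of treatment. Many listed variables (previous comorbidities, age, height, duration of diabetes, previous treatment) belong at index. On that reading no truncation arises and only the contradiction is left. This stands, but the sentence would still have to go, since it is the protocol's operative analysis instruction. Co-medication, HbA1c, weight and hospitalisations could well be tabulated over time.

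Three further points also stand. The section 6 milestone table has no rows in the available text, so a cut date may be given there. The 100% for Cohorts 1 and 2 is calendar opportunity only; how often the registries record values is unknown. The category in section 9.7.2 for values not reported might, if used per period, make falling numbers visible, but it would not correct the mix or separate missing values from time not yet elapsed.

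A reader might infer that all later Cohort 3 figures describe only its earliest starters. At the central cut that is literal for the last one or two half-years; before that it is a gradual narrowing, with 62% still able to complete the second. A reader might also infer that later comparisons must understate the difference between cohorts. That needs a trend within Cohort 3 in the same direction as the difference, and the third case above gives the opposite.

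**Conclusion.** The contradiction is established from the text: section 9.7.1 and the abstract's data analysis entry cannot be reconciled with section 9.1, the abstract's design and variables entries, or the checklist comment, and item 4.2.5 points to a duration that section 9.2 lacks.

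The truncation is conditional on half-yearly tables being produced. The shares rest on an assumed cut and start pattern, but for every cut tried Cohort 3 loses patients sooner and more heavily than the other cohorts. The sizes of the drift and of the distorted differences are illustrations; the protocol gives no cohort sizes or expected trends. Section 9.7.1 does not say whether the group tests are repeated per half-year.

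It would be wrong to conclude that the main objective is compromised. The comparison at index keeps every Cohort 3 patient and is not affected. The point should be settled before programming, and it does not invalidate the study.

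**What to change.** Make the between-cohort comparison at index, and bring section 9.7.1 and the abstract's data analysis entry into line with section 9.1, the abstract's design and variables entries and the checklist comment.

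- **If the study is baseline only:** delete the half-yearly sentence in both places and correct checklist item 4.2.5.
- **If half-yearly tables are kept:** state the data cut. Limit the tables to patients whose index date allows a common potential follow-up, for example 12 months. Report the number eligible and the number with data per period and cohort. An index-date filter equalises opportunity only, and under complete-case analysis the patients with values still differ by period, so describe change only in patients with values at both time points. Show no cohort tests or pooled total beyond the common horizon.

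The cost is protocol wording, an index-date filter and some counts. A 12-month table omits about 38% of Cohort 3 (1 − 0.62) at the central cut with uniform starts, 46% if the start rate doubles, and 36% to 51% across the range of cuts with uniform starts. These patients remain in the index comparison.

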8. RESEARCH QUESTION AND OBJECTIVES

Description of the real-life treatment of adult patients with T2DM receiving empagliflozin, comparing the characteristics of patients starting Empagliflozin in three time intervals:

- The first analysis will include the patients receiving Empagliflozin before the EMPA-REG-OUTCOME study was published (time until mid-Sept. 2015; "Cohort 1").
- The second analysis will include patients receiving Empagliflozin starting from the EMPA-REG-OUTCOME study being published until CV Label Change (time from mid-Sept. 2015-mid-Jan. 2017; "Cohort 2").
- The third analysis will include all patients receiving Empagliflozin starting from mid-Jan. 2017 ("Cohort 3") until last available data cut.

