9.6 DATA MAIN MANAGEMENT

The medical team (

will be responsible for data management, including quality checking of the data. It is pointed out that no individual patient data will be used in this study and that data will only be presented in aggregated form.

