9.9 LIMITATIONS OF THE RESEARCH METHODS

DPV & DIVE data are observational data; treatment, especially the use of Empagliflozin, is not randomized to the patients. This has to be kept in mind for the interpretation of the results. Also, a systematic difference (bias) between patients documented in the registry versus patients treated at facilities not participating in either of the registries cannot be entirely excluded.

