9.10 SUBJECTS

All patients with T2DM from the DPV & DIVE registries receiving Empagliflozin will be included. The patients will be divided in three cohorts based on the time point of Empagliflozin treatment start to better identify the differences between these cohorts.

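### DPV and DIVE are pooled with no by-registry output, so a pooled cohort difference cannot be told apart from a change in registry mix (test wording for three cohorts: a separate, minor clarification)

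*Combined protocol and SAP*

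**What the plan says.** The objective in section 8 is "comparing the characteristics of patients starting Empagliflozin in three time intervals", and section 9.10 adds: "The patients will be divided in three cohorts based on the time point of Empagliflozin treatment start". Section 9.1 describes two deliveries, "An anonymized dataset will be delivered by DIVE and DPV, respectively", followed by "The two datasets will then be combined". Section 9.7.1 repeats the merging and plans output "for total study population and separated by study cohort".

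On testing, section 9.7.1 and the abstract state: "Group comparison will be based on Wilcoxon rank sum test (continuous variables"), with a chi-square test for binary and categorical variables. The primary outcomes in section 9.3.1.1 are percentages with a previous condition, plus co-medication. Most continuous variables are secondary (section 9.3.1.2).

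Sections 9.9 and 9.11 name one selection issue, "a systematic difference (bias) between patients documented in the registry versus patients treated at facilities not participating in either of the registries". Neither mentions a possible difference between DPV and DIVE. No section plans a by-registry table, a registry stratum, or a count of patients by registry and cohort.

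**The concern.** The central question is whether patients starting empagliflozin differ between three calendar periods. A pooled percentage is a weighted average of two registry percentages, and the weights are the registry shares in that cohort. If the shares move between periods and the registries differ in the variable, the pooled figure moves even when neither registry changes. It can also stay flat when both registries change. The primary outcomes are exposed to this because they are pooled percentages.

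The documents give some reason to check. DMP participation and hospitalizations come from DPV only (section 9.3.1.2). DPV centres are described as predominantly in Germany and Austria, while DIVE is described as national (section 9.4). This does not show that any shared variable differs between the registries. It does mean that interchangeability should be demonstrated rather than taken for granted.

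**Working it through.** **1. Is there a planned output that would separate the two explanations?** Section 9.7.1 gives total and cohort only. In Annex 2, item 10.3 (stratified analyses) is ticked Yes and points to 9.7.1, where the only split is by cohort. Item 10.4 (adjustment for confounding) is ticked Yes and points to 9.8, which covers code checking and plausibility review and contains no adjustment method. Item 7.1 marks confounding as not applicable. So there is no such output.

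**2. Inputs.** From the documents: about 7,900 patients (section 9.5) and three cohorts. There is no sample-size calculation to reproduce, since checklist item 10.6 is marked not applicable. Everything else is assumed: prevalence in each registry, DPV share per cohort, cohort sizes, and a 5% reference level used only for illustration.

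**3. Size of the mix effect.** With no change inside either registry,

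pooled prevalence = s × p(DPV) + (1 − s) × p(DIVE), where s is the DPV share,

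so change from Cohort 1 to Cohort 3 = gap × shift in s. For example, 10 points × (0.60 − 0.40) = 2.0 points.

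| Registry gap | DPV share 45/50/55% | 40/50/60% | 30/50/70% |
|---|---|---|---|
| 10 points | 1.0 | 2.0 | 4.0 |
| 4 points | 0.4 | 0.8 | 1.6 |
| 2 points | 0.2 | 0.4 | 0.8 |

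With no gap or no shift the effect is 0.

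**4. How often the pooled chi-square test would fall below 5%.** Noncentral chi-square, 2 df, mean prevalence 30%. The noncentrality is Σ n(p − p̄)² / [p̄(1 − p̄)]. The two figures are for the 10/30/60% cohort split (790/2,370/4,740) and for equal cohorts.

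| Registry gap | 45/50/55% | 40/50/60% | 30/50/70% |
|---|---|---|---|
| 10 points | 8–10% | 20–27% | 63–82% |
| 4 points | 5–6% | 7–8% | 14–19% |
| 2 points | 5% | 5–6% | 7–8% |

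These are not bounds. With a 5/25/70% split (395/1,975/5,530) the 10-point row becomes 7%, 15% and 49%. With the 10/30/60% split and half the records complete it becomes 7%, 12% and 35%. At 10% prevalence a 4-point gap gives 6–7%, 10–13% and 27–39%. Changing the cohort sizes alters these rates but not the point sizes in step 3.

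**5. Masking.** Suppose DPV is 10 points above DIVE, prevalence rises 2 points in both (DPV 34% to 36%, DIVE 24% to 26%), and the DPV share falls from 60% to 40%. Cohort 1: 0.6 × 34 + 0.4 × 24 = 30.0%. Cohort 3: 0.4 × 36 + 0.6 × 26 = 30.0%. The pooled change is 0.0; the Mantel-Haenszel difference stratified by registry is 2.0 points.

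**6. The rank test, separately.** Three cohorts give three possible pairs. Three unadjusted rank sum tests at an assumed 5% each have a per-variable chance of at least one false positive of about 11–12% (0.122 for equal cohorts, 0.118 for 10/30/60%, 0.114 for 5/25/70%). A single three-group test keeps it at 5%. The chi-square test already extends to three groups.

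**The case against.** The strongest reply is that the pooled percentages answer the stated question. The objective is to describe who starts empagliflozin in each period, and the pooled figures describe the combined registry population correctly. If prescribing moves between the settings that the two registries cover, that is a real change in who starts treatment, and a stratified test would condition it away. This stands. It is why the stratified analysis belongs beside the pooled one and should not replace it.

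Second, the study is descriptive. Checklist item 2.1.4 (hypotheses) is marked not applicable, item 2.1.5 (no a priori hypothesis) is ticked Yes, and no significance level is stated. This also stands, and it makes the point sizes the better measure than the rejection rates. It does not remove the concern, because registry mix moves the descriptive percentages themselves.

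Third, the analyst knows both registries and the medical team reviews plausibility (sections 9.7.1 and 9.8). That is some safeguard, but not an output that a reader can check.

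Two further inferences are tempting. A reader might conclude that the rank sum test is wrong for this study. It is not: pairwise rank sum tests are valid, and the plan merely leaves the pairs unstated. A reader might also take "data will only be presented in aggregated form" in section 9.6 as ruling out a registry breakdown. That sentence concerns individual patient data, and by-registry tables are aggregates too.

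**Conclusion.** The gap is real and inexpensive to close. As written, the plan produces nothing that would show whether a pooled cohort difference arose within the registries or from their mix, and the bias sections do not raise the question.

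A reader might infer that the pooled results will be distorted. The documents do not support that: they give neither registry shares by cohort nor any shared variable by registry. The effect is negligible when the gap or the shift is small (at most 0.8 points with a 2-point gap) and becomes material only when both are sizeable (2.0 to 4.0 points with a 10-point gap and a shift of 20 to 40 points). All of these inputs are assumed.

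The rank-test wording is under-specification. It does not reach the primary percentages tested by chi-square, and it plays no part in the registry-mix problem.

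**What to change.** Keep the pooled comparison as the description of the combined registry population, and add to section 9.7.1:

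- patient counts by registry and cohort;
- the main tables by registry, for variables recorded in both registries;
- for those variables, a registry-stratified comparison beside the pooled one: the Cochran-Mantel-Haenszel general association test with the Mantel-Haenszel risk difference for percentages, and a van Elteren-type rank test for continuous variables.

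Leave DPV-only variables (DMP participation, hospitalizations) unstratified. For FPG and empagliflozin dosage, marked as available in a subgroup only, state which registry or registries supply them and apply the same rule. Add a sentence on possible DPV/DIVE differences to sections 9.9 and 9.11.

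Separately, state in section 9.7.1 and the abstract either that Kruskal-Wallis is used for the three-cohort comparison or which pairs the rank sum test compares.

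The cost is protocol wording, a few more tables and a little SAS programming. Each registry delivers its own dataset, so registry of origin is already known and no new data are needed. The pooled test loses nothing, because the stratified one is added to it. Where the registries do not differ, the stratified test had 0 to 5 points less power than the pooled one in the scenarios simulated (true 3-point rise). Shifts in centre mix within a registry remain unaddressed and should be named as a limitation.

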9.3.1.1 Primary outcomes

- Previous occurrence (percentages) of
 - Typical CV comorbidities:
 - MI
 - Stroke
 - CAD
 - PAD
 - CHF (form (HFrEF/ HFpEF)

Proprietary confidential information © 2020 Boehringer Ingelheim International GmbH or one or more of its affiliated companies

- Other typical diabetes complications:
 - Neuropathy
 - Nephropathy / Renal function (eGFR, micro-/ macroalbuminuria)
 - Diabetic foot syndrome
 - Retinopathy (background and proliferative)
- Antidiabetic and cardiovascular co-medication (lipid-lowering agents, RAAS blockers, other antihypertensives, beta blockers, diuretics, antiplatelets and anticoagulants)

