1.1 Does the protocol specify timelines for				
1.1.1 Start of data collection ¹				6
1.1.2 End of data collection ²				6
1.1.3 Study progress report(s)				-
1.1.4 Interim progress report(s)				-
1.1.5 Registration in the EU PAS register				-
1.1.6 Final report of study results.				6

Comments:

Section 2: Research question	Yes	No	N/A	Section Number
2.1 Does the formulation of the research question and objectives clearly explain:				8
2.1.1 Why the study is conducted? (e.g. to address an important public health concern, a risk identified in the risk management plan, an emerging safety issue)				7
2.1.2 The objective(s) of the study?				8
2.1.3 The target population? (i.e. population or subgroup to whom the study results are intended to be generalised)				9.2
2.1.4 Which hypothesis(-es) is (are) to be tested?				-
2.1.5 If applicable, that there is no a priori hypothesis?				7

Comments:

Section 3: Study design	Yes	No	N/A	Section Number
3.1 Is the study design described? (e.g. cohort, case-control, cross-sectional, new or alternative design)				9.1
3.2 Does the protocol specify whether the study is based on primary, secondary or combined data collection?				9.1

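### Cohort percentages are planned, but section 9.7.1 specifies the comparison between cohorts only as tests, with no effect measure or confidence interval, although checklist item 3.4 says section 9.7 gives one

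*Combined protocol and SAP*

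**What the plan says.** The objective in section 8 is to compare the characteristics of patients who start empagliflozin in three calendar periods, divided by the publication of the outcome trial and by the CV label change.

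Section 9.7.1 describes two activities:

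- Description: "nonparametric descriptive analyses will be used", with variables assessed "for total study population and separated by study cohort".
- Comparison: "Group comparison will be based on Wilcoxon rank sum test (continuous variables") and "X²-test for binary/categorial values".

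It names no effect measure, no confidence interval and no specific pair of cohorts.

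Section 9.3.1.1 defines the primary comorbidity outcomes as "Previous occurrence (percentages) of" individual conditions. Under "Typical CV comorbidities" it lists MI, stroke, CAD, PAD and CHF separately, with no combined item.

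Three checklist answers in Annex 2 bear on this. Item 3.4, "3.4 Does the protocol specify measure(s) of association", is ticked Yes with a pointer to section 9.7. Item 2.1.4, "2.1.4 Which hypothesis(-es) is (are) to be tested", is marked not applicable. Item 2.1.5, that there is no a priori hypothesis, is ticked Yes. Section 9.5 gives only a total of about 7,900 patients.

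**The concern.** A study that declares no hypothesis and sets out to describe change over time needs estimates of that change with their precision. The only tools prescribed for the between-cohort step are significance tests, and a p-value mixes the size of the change with the number of patients in each cohort. If the cohorts differ in size, equal shifts across the two boundaries can produce quite different p-values. A report built on them could suggest that one boundary mattered and the other did not. The checklist meanwhile tells its reader that section 9.7 already contains a measure of association.

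A second, smaller matter concerns the CV items. Both boundaries are CV events, so the share of starters with any CV disease is a natural summary. The five conditions overlap within patients, so that share cannot be worked out from five separate percentages.

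**Working it through.** **Text check.** Setting section 9.7 beside checklist item 3.4: the section contains two named tests, descriptive analysis by cohort, the complete-case rule and the plausibility ranges. It contains no difference, ratio or interval. Item 3.4 therefore points to something that is not there.

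**Plan's own figure.** The total of about 7,900 comes without alpha, power, effect size or split, so there is nothing to reproduce.

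**Inputs for the illustration.**
- Total of 7,900: section 9.5.
- Cohort windows: section 8. Cohort 2 runs from mid-September 2015 to mid-January 2017, which is 16 months. Cohort 3 runs from mid-January 2017 to the last data cut. If the cut is assumed to be 1 September 2019, the planned start of data access, that is about 31.5 months. No start date is given for Cohort 1.
- Cohort sizes: assumed. 5/25/70% gives 395, 1,975 and 5,530; 10/30/60% gives 790, 2,370 and 4,740; equal cohorts have 2,633 each.
- Prevalences: assumed at 27%, 30% and 33%, which is the same 3-point step twice.

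**Pairwise tests.** z = d / sqrt[p̄(1 − p̄)(1/n1 + 1/n2)], where p̄ is the pooled prevalence. At 5/25/70%:
- Cohort 1 to 2: p̄ = 0.295, standard error 0.0251, z = 0.03/0.0251 = 1.19, p = 0.23.
- Cohort 2 to 3: p̄ = 0.322, standard error 0.01225, z = 0.03/0.01225 = 2.45, p = 0.014.

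| Assumed split | Cohort 1 to 2 | Cohort 2 to 3 |
|---|---|---|
| 5/25/70% | p = 0.23 | p = 0.014 |
| 10/30/60% | p = 0.11 | p = 0.011 |
| Equal | p = 0.016 | p = 0.019 |

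**The same steps as estimates.** 95% CI = d ± 1.96 × sqrt[p1(1 − p1)/n1 + p2(1 − p2)/n2]. At 5/25/70%:
- Cohort 1 to 2: 3.0 ± 1.96 × 2.46 = 3.0 ± 4.8 points, so −1.8 to 7.8.
- Cohort 2 to 3: 3.0 ± 1.96 × 1.21 = 3.0 ± 2.4 points, so 0.6 to 5.4.

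The point estimates are identical and only the precision differs. The p-values alone do not show this.

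**Smallest difference reaching p < 0.05 at 30% prevalence.** 1.96 × sqrt[0.21 × (1/n1 + 1/n2)] is 2.5 points with equal cohorts. Against a Cohort 1 of 395 it is 5.0 points for Cohort 2 and 4.7 points for Cohort 3.

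**Any CV disease.** The share with at least one of five conditions lies between the largest single percentage (complete nesting) and the sum (no overlap). With illustrative percentages of 10, 8, 22, 9 and 10, that is 22% to 59%. The upper end is a mathematical limit that real overlap would not reach. The point is only that the separate items do not fix the value.

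**The case against.** The strongest reply is that the size of each change will be visible. Primary comorbidities are percentages, and section 9.7.1 reports results by cohort. In the example above a reader would see 27, 30 and 33%, could subtract, and could compute an unadjusted interval if denominators are printed. This stands. A reader might infer from the test-only sentence that the study yields nothing but p-values or cannot say how much the profile of starters changed. The documents do not support that reading. The gap is a prespecified, reported effect measure with its interval. For continuous items, a Hodges-Lehmann shift and its interval cannot be rebuilt from published medians.

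The illustration also needs rules that the plan does not contain: unequal cohorts, tests of adjacent pairs, and a reading of p-values against 0.05. A single three-cohort chi-square on the same prevalences gives p = 0.005 at 5/25/70% and p = 0.0006 at 10/30/60%, and with equal cohorts the pairwise asymmetry disappears. Unequal windows make unequal cohorts plausible, but the protocol does not state cohort sizes. All of this stands and limits how much weight the numbers can carry.

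On the composite, no section promises an any-CV item, and the primary outcomes also cover other diabetes complications and co-medication. Its absence is therefore not an error, and nothing in the documents requires it to lead the comparison.

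Finally, the checklist describes itself as a supporting document and the study is not a PASS, so the mismatch in item 3.4 is minor taken alone. It does show that an effect measure was thought to be in place.

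**Conclusion.** The point holds in a limited form. Description by cohort is planned. The comparison between cohorts is specified only as Wilcoxon and chi-square tests, and section 9.7 has no effect measure or confidence interval, contrary to checklist item 3.4. That part rests on the text alone.

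The size of the consequence rests on assumptions. With cohorts of 395, 1,975 and 5,530, a prevalence of 27, 30 and 33% and adjacent pairwise tests, equal 3-point steps give p = 0.23 and 0.014. With equal cohorts, p = 0.016 and 0.019. The documents do not settle which situation applies.

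This should be changed because estimation suits a study with no a priori hypothesis and costs almost nothing. It does not invalidate the planned tables.

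**What to change.** In section 9.7.1:

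- Name the cohort contrasts, for example 1 versus 2 and 2 versus 3. This also settles how a two-group rank sum test is applied to three cohorts.
- Report each contrast as a difference with a 95% CI: difference in percentages for binary items and for each level of categorical items such as age group, and the Hodges-Lehmann shift for continuous items.
- Keep the Wilcoxon and chi-square tests as supportive, and print the denominators.

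In Annex 2, make the answer to item 3.4 agree with the revised section 9.7.

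Optionally, add to section 9.3.1.1 one derived item, any of MI, stroke, CAD, PAD or CHF. It need not be the lead comparison.

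The cost is a few sentences, standard SAS output and, if the option is taken, one derived variable. No new data are needed.
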